9.5.4 Analysis of DLTs

To meet the study primary objective of determining the MTD/ biologically active doses of CORT125281 in combination with enzalutamide, the number, percent and duration of DLTs according to the NCI-CTCAE, version 4.03, will be summarized by CORT125281 dose and overall.

The DLT rate per patient-weeks, defined as the number of DLTs normalized to the total duration of exposure (in weeks) to CORT125281 during the DLT-evaluation period for all patients in the same treatment arm, will also be presented.

Analyses of DLTs will be performed in the DLT-Evaluable Population.

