9.9 Interim Safety Analyses

In Dose-Determination Segment 1, the DRC will make recommendations regarding escalation to the next planned dose, repeating a prior dose, or investigating other dose cohorts (ie, intermediate or lower doses) until the MTD/RD is identified (Section 5.4.1). If a biologically active dose is determined as defined by the dose level at which CORT125281 has been demonstrated to inhibit GR and at which the DLT rate is <33%, the Dose-Determination Phase may be completed prior to the determination of the MTD, per the recommendation of the DRC.

In Dose-Determination Phase Segment 2 (Section 5.4.2), after all patients complete 3 cycles of treatment or discontinue treatment, the data will be unblinded and the DRC will meet to review the safety and available PK and PD data. The DRC will evaluate the frequency of DLTs, the DLT rate (number of DLTs per week [7-day period] during the DLT-evaluation period), and overall tolerability to determine the feasibility of the dose titration regimen for the Phase 2 RD.

In the Expansion Phase, an interim safety analysis will be conducted after a total of 20 patients complete 3 cycles of therapy.

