7.4. Handling of Missing Data

Missing data will not be imputed unless otherwise specified. Missing dates or partially missing dates will be imputed conservatively for adverse events and prior/concomitant medications/procedures.

For safety analyses, incomplete date of last dose of study drug and incomplete start date of a new antitumor treatment that are missing the day of the month, the 15th of the month will be used to impute the missing data. When imputing partial last dose dates, the last assessment date and death date will be taken into consideration. This imputation rule will be used to determine the treatment-emergent period.

Adverse Events

The imputation rule for the safety analyses will be used to address the issues with partial dates. The imputed dates will be used to determine the treatment-emergent period. For adverse events with a partial date, available date parts (year, month, and day) of the partial date will be compared with the corresponding date components of the start date and end date of the treatment-emergent period to determine if the event is treatment emergent. When in doubt, the adverse event will be considered treatment emergent by default. The following rules will be applied to impute partial dates for adverse events:

If start date of an adverse event is partially missing, impute as follows:

- If both month and day are missing and year = year of treatment start date, then set to treatment start date
- If both month and day are missing and year \neq year of treatment start date, then set to January 01
- If day is missing and month and year = month and year of treatment start date, then set to treatment start date
- If day is missing and month and year \neq month and year of treatment start date, then set to first of the month
- If only year is missing or start date is completely missing, set to treatment start date as long as adverse event end date is not before treatment start date

If end date of an adverse event is partially missing, impute as follows:

- If both month and day are missing, then set to December 31
- If only day is missing, then set to last day of the month
- If only year is missing or end date is completely missing, do not impute

Concomitant Medications

When the start date or end date of a medication is partially missing, the date will be imputed to determine whether the medication is prior or concomitant (or both). The following rules will be applied to impute partial dates for medications:

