One patient may experience more than one DLTs during the DLT evaluation period. Maximum Duration of DLTs will be calculated in weeks and is defined as the End Date of DLT – Start Date of DLT for the longest DLT time duration for each subject. Number of patients with at least 1 DLT, number of DLTs, and maximum duration of DLTs will be summarized by study regimen and overall.

DLT rate per patient-week will also be summarized by study arm, study regimen and overall, where the numerator is the number of patients with at least 1 DLT, and the denominator is the sum of patient's treatment duration (in weeks) during the DLT-evaluation period which is calculated as the days of the patients on treatment during the first 12 weeks divided by 7.

Number of patients with at least 1 DLT and number of DLTs will also be summarized by study arm, highest exicorilant dose level received, and overall.

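### SAP 8.8 has no rule for the duration of an ongoing DLT, so unresolved DLTs fall out of the maximum-duration line and probably bias it short; DLT counts, DLT rates and the MTD rule are unaffected

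*SAP*

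**What the plan says.** Protocol 9.5.4, serving the primary objective, asks that "the number, percent and duration of DLTs according to the NCI-CTCAE, version 4.03, will be summarized", by dose and overall. Duration is thus a required output.

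SAP 8.8 implements it for Segment 2 only: "Maximum Duration of DLTs will be calculated in weeks and is defined as the End Date of DLT" less the start date, in weeks, for the longest DLT in each patient. It does not mention a DLT without an end date.

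SAP 7.4 sets the default: "Missing data will not be imputed unless otherwise specified". Its rules for adverse event end dates are:

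- day missing: "If only day is missing, then set to last day of the month"
- month and day missing: "If both month and day are missing, then set to December 31"
- otherwise: "If only year is missing or end date is completely missing, do not impute"

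The stated purpose of these rules is classification: "The imputed dates will be used to determine the treatment-emergent period". DLT duration is not mentioned.

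For Segment 2, Protocol 9.9 says that "after all patients complete 3 cycles of treatment or discontinue treatment, the data will be unblinded and the DRC will meet". Protocol 8.1.2 and 8.1.2.1 allow follow-up of an adverse event to stop once it is stable, so a persistent DLT may never acquire an end date.

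**The concern.** An end-minus-start duration exists only for events that have ended. With no imputation of an absent end date and no censoring rule, the DLTs without a duration are the unresolved ones, and these tend to be the long ones. The missingness is informative, and the remaining values describe resolved DLTs under a label that promises the maximum.

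What is at stake is how reversible the toxicity looks. In Segment 2 the DRC weighs overall tolerability beside DLT frequency and rate. A short maximum duration computed from resolved events alone could make persistent toxicity look brief.

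The omission looks like an oversight. SAP 9.1 writes censoring rules for rPFS, DOR, clinical and bone progression, SSE and OS, and adds one day in its rPFS, DOR and OS formulas, as SAP 8.7 does for exposure. The DLT duration has neither, and SAP 13 does not list it as a change from the protocol.

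**Working it through.** The plan states no figure for DLT duration, so there is nothing to reproduce. The check has three parts.

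**1. Which DLT outputs need an end date?**

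| Output | Place | Needs end date? |
|---|---|---|
| Patients with a DLT; number of DLTs | SAP 8.8 | No |
| DLT rate by arm and regimen | SAP 8.8 | No |
| DLT rate per patient-week | SAP 8.8 | No |
| DLT evaluability | SAP 6.3 | No |
| MTD rule (DLT rate below 33%) | Protocol 5.6, SAP 4.1 | No |
| Maximum duration | SAP 8.8 | Yes |

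Only the last row is affected.

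**2. Worked example (event data assumed).** Arm A has 12 evaluable patients (Protocol 3.2.1). Suppose 4 have one DLT each: three resolved after 1, 2 and 3 weeks, one ongoing at 8 weeks.

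- Resolved only: mean (1 + 2 + 3)/3 = 2.0 weeks, median 2.0, on 3 patients.
- Ongoing DLT counted to the cut, a lower bound: mean (1 + 2 + 3 + 8)/4 = 3.5 weeks, median 2.5, on 4 patients.
- DLT rate either way: 4/12 = 33.3%. Per patient-week, with 12 weeks on treatment each: 4/(12 × 12) = 0.028.

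For one patient with a resolved 3-day DLT and another ongoing at 60 days, the text supports a maximum of 3 days or a missing value. The true maximum is at least 60 days.

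**3. Possible size.** The documents give no DLT durations, onset times or accrual rate, so everything here is assumed. Each simulated patient has one DLT, so the DLT and the patient maximum coincide.

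*(a) Every DLT resolves.* Duration is exponential with mean m weeks, onset uniform over weeks 0 to 12, and the cut is c weeks after the patient's own first dose. The share ongoing is (m/12)[exp(−(c−12)/m) − exp(−c/m)]. For m = 4 and c = 12 this is (1/3)(1 − e⁻³) = 0.317. Cells show the simulated resolved-only mean in weeks, with the share ongoing.

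| True mean | c = 12 | c = 16 | c = 24 | c = 52 |
|---|---|---|---|---|
| 2 | 1.61 (17%) | 1.86 (2%) | 2.00 (0%) | 2.00 (0%) |
| 4 | 2.44 (32%) | 3.03 (12%) | 3.76 (2%) | 4.00 (0%) |
| 8 | 3.12 (52%) | 4.08 (31%) | 5.83 (12%) | 7.84 (0.3%) |

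*(b) Staggered entry.* Entry is uniform over 180 days, onset uniform over 84 days from entry, mean duration 28 days, and the cut is 84 days after accrual ends.

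- All resolve: share ongoing (28/180)(1 − e^(−180/28)) × (28/84)(1 − e⁻³) = 0.155 × 0.317 = 4.9%. Resolved-only median 18.2 days against 28 ln 2 = 19.4 (−6%).
- 15% never resolve: share ongoing 0.15 + 0.85 × 0.049 = 19.2%. Resolved-only median 18.2 days against −28 ln(1 − 0.5/0.85) = 24.8 (−27%). Resolved-only mean 25.4 days against 42.5 with ongoing DLTs counted to the cut (−40%).
- 90 more days of follow-up: the first share falls to 4.9% × e^(−90/28) = 0.2%, the second only to 0.15 + 0.85 × 0.002 = 15.2%.

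Varying mean duration over 14 to 56 days, the never-resolving share over 0 to 30% and accrual over 0 to 12 months, the share without a duration runs from about 1% to 66%, and the median is understated by 1% to 75%.

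**Two smaller effects.** Without the added day, a DLT starting and ending on the same date has duration 0 instead of 1/7 = 0.14 week. In the other direction, if the SAP 7.4 rule is applied to duration, a day-missing end date moved to month end adds (0 + 1 + … + 29)/30 = 14.5 days on average, assuming a 30-day month and a uniform end day.

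**The case against.** The strongest reply is that only one descriptive line is touched and no decision rule uses it. The MTD rule is a rate, and the DRC is charged with DLT frequency, DLT rate and overall tolerability; nothing says it must read tolerability from this line. SAP 10.1 lists every adverse event with its ongoing status, and with about 16 evaluable patients a persistent DLT would be visible there. Related events are followed until resolved or stable, and the study-report analyses come after database closure, later than the DRC cut. All of this stands, and it limits the importance of the point. It does not supply a duration for a DLT judged stable and never closed.

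It is also fair to say that the SAP is silent and does not direct anyone to drop ongoing DLTs. A missing maximum for the patient fits the text as well as a maximum over resolved events. Under either reading the long value is absent.

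A reader might infer that unresolved DLTs vanish from the primary DLT summary as a whole, or that end dates are never imputed. The documents do not support either. Counts and rates rest on occurrence, an unresolved DLT still makes the patient evaluable, and partial end dates are imputed late, which can lengthen durations. Nor is it supported that the timing of the DRC review makes ongoing DLTs common. In the staggered-entry model with all DLTs resolving, that timing leaves 4.9% ongoing; 15 of the 19.2 points in the other case are simply the assumed never-resolving share.

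**Conclusion.** The gap is real and confined to the maximum-duration line. An ongoing DLT has no computable duration under SAP 8.8 and 7.4, and the line is probably biased short when persistent DLTs occur. Understatement is likely but not certain: it requires some DLTs to be unresolved at the cut and to be the longer ones, and late-imputed partial dates push the other way.

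No single percentage should be quoted as the bias. The documents contain no duration or accrual data, and the assumed scenarios run from negligible to large. The two drivers are how early the data are cut and whether any DLTs never resolve; longer follow-up cures the first but not the second. The omitted day is a matter of consistency, at 0.14 week in a quantity rounded to one decimal place. DLT counts, both DLT rates, evaluability and the MTD rule stand as planned.

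The change is worth making before the analysis because duration is a protocol-named summary for the primary objective and the correction is cheap.

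**What to change.** In SAP 8.8:

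- Define DLT duration as (end date − start date + 1)/7 weeks, in line with the SAP's other durations.
- Count a DLT without an end date to the earliest of data cutoff, death or last contact, treat it as censored, and show it as ≥ x weeks. SAP 9.1 already derives a last-contact date for OS.
- Take the patient's maximum over resolved and ongoing DLTs together.
- Report the number and percent of DLTs ongoing beside the duration summary.
- State whether the SAP 7.4 imputation of partial end dates applies to duration.
- State whether duration will also be given for Segment 1, since Protocol 9.5.4 asks for it by dose and overall.

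A Kaplan-Meier median is optional; with the few DLTs expected in 12 + 4 patients it may not be estimable.

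The cost is a few sentences of SAP text and minor programming. No new data are needed, because ongoing status is already to be listed.

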During the double-blind portion of the Dose-Determination Phase (ie, Segment 2), an unblinded Medical Monitor independent of the study team will provide additional oversight for the study, including review of serious unexpected AEs considered related to either CORT125281 or enzalutamide and DLTs.

The DLT-evaluation period will extend from the first dose of CORT125281 through the completion of Cycle 3. The DLT-Evaluable Population will include all patients in Segment 2 who received at least 1 dose of CORT125281 and fulfilled at least 1 of the following:

- Completed 3 cycles of treatment with CORT125281 + enzalutamide and received at least 75% of the study regimen
- Experience a DLT

Patients who are non-evaluable for DLTs will include the following:

- Received <75% of the study regimen for reasons other than toxicity
- Patients who withdraw from the study prior to completion of Cycle 3 for reasons other than toxicity (eg, lost to follow-up, withdrawal of consent, or disease progression)

Patients who are non-evaluable for DLTs will be allowed to continue in the study and receive CORT125281 in combination with enzalutamide. Patients who are non-evaluable for DLTs may be replaced to allow a sufficient number of patients to evaluate DLTs (Section 9.4.1).

After all patients complete 3 cycles of treatment or discontinue treatment, the data will be unblinded and the DRC will meet to review the safety and available PK and PD data. The DRC will evaluate the frequency of DLTs, the DLT rate (number of DLTs in DLT-evaluable patients per week [7-day period] during the DLT-evaluation period), and overall tolerability in their assessment of the dose titration regimen as the Phase 2 RD.

If the DLT rate for the regimen is $\geq 33\%$, alternative titration schemes may be considered as the regimen for the RD, such as greater time increments between dose escalations or limiting the upper range of the regimen to those dose levels corresponding to a DLT rate of $< 33\%$. Once the DRC has determined the RD, patients assigned to Arm B who have not experienced dose reductions due to toxicity will then escalate the CORT125281 dose per the recommended upward titration regimen.

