5.7.1.1 Continuation of Enzalutamide After CORT125281 Interruption/Discontinuation

The following guidelines apply for enzalutamide continuation in patients who discontinue CORT125281 or have a CORT125281 dosing interruption:

1. Patients may resume enzalutamide prior to resuming CORT125281 after the Investigator discusses with the Medical Monitor. The intent is for patients to maintain the dose intensity of enzalutamide per standard practice whenever possible.
2. For patients who have not progressed on enzalutamide or second-generation anti-androgen, if CORT125281 is discontinued, enzalutamide will be continued. Following the visit of the subsequent cycle (after discontinuing CORT125281), if all toxicities attributed to CORT125281 have resolved, study visits will occur at least every third cycle until discontinuation of enzalutamide (Section 7.3.1). Upon discontinuation of enzalutamide, the patient will return for the EOT and EOT +30 Days Visits.
3. Patients previously progressing on enzalutamide or second-generation anti-androgen will discontinue enzalutamide, if CORT125281 is discontinued.

Radiographic tumor assessments (CT/MRI, bone scan) should be continued until disease progression per the SoA (Table 16).

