Dose Level	Resulting exicorilant Dosage (QD)		Open-Label Bottle (exicorilant)	Blind-Label Bottle (exicorilant or Placebo) ^a
	Arm A	Arm B		
1 (Starting Dose)	240 mg	240 mg	6 capsules	0 capsules
+1 (First Increase)	280 mg	240 mg	6 capsules	1 capsule
+2 (Second Increase)	320 mg	240 mg	6 capsules	2 capsules

QD, once daily.

Note: The exicorilant dosage will be escalated in 2-week intervals unless there are intolerable Grade 2 toxicities, dose-limiting toxicities, or Grade 3 or greater toxicities attributed to exicorilant (Protocol Section 5.7).

^a Note: The blind-label bottle contains blinded capsules (exicorilant [Arm A] or placebo [Arm B]). During the double-blind portion of the Dose-Determination Phase (ie, Segment 2), an unblinded Medical Monitor independent of the study team will provide additional oversight for the study, including review of serious unexpected adverse events (AEs) considered related to either exicorilant or enzalutamide and DLTs.

After all patients complete 3 cycles of treatment or discontinue treatment, the data will be unblinded and the DRC will meet to review the safety and available PK and PD data. The DRC will evaluate the frequency of DLTs, the DLT rate (the number of DLTs per week [7-day period] during the DLT-evaluation period), and overall tolerability in their assessment of the dose titration regimen as the Phase 2 RP2D. If the DLT rate for the regimen is $\geq 33\%$, alternative titration schemes may be considered as the regimen for the RP2D, such as greater time increments between dose escalations or limiting the upper range of the regimen to those dose levels corresponding to a DLT rate of $< 33\%$. Once the DRC has determined the RP2D,

patients assigned to Arm B who have not experienced dose reductions due to toxicity will have their exicorilant dose escalated per the recommended Phase 2 regimen.

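### SAP 8.8 computes the Segment 2 DLT rate per patient-week from patients rather than DLTs, contrary to protocol 9.5.4 and SAP 2.3, and does not declare the change

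*SAP*

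**What the plan says.** The definitions of the rate, side by side:

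- **Protocol 9.5.4** has the rate per patient-weeks "defined as the number of DLTs normalized to the total duration of exposure (in weeks) to CORT125281 during the DLT-evaluation period", pooled over the patients in an arm.
- **Protocol 5.4.2**, on what the Data Review Committee (DRC) evaluates in Segment 2: "number of DLTs in DLT-evaluable patients per week [7-day period] during the DLT-evaluation period". Protocol 9.9 also counts DLTs per week.
- **SAP 2.3** repeats this for the DRC review: "the DLT rate (the number of DLTs per week [7-day period] during the DLT-evaluation period".
- **SAP 8.8** gives the rate to be programmed: "where the numerator is the number of patients with at least 1 DLT, and the denominator is the sum of" the patients' treatment durations, "calculated as the days of the patients on treatment during the first 12 weeks divided by 7".

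The paragraph of SAP 8.8 just before that definition recognises repeat events: "One patient may experience more than one DLTs during the DLT evaluation period".

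SAP section 13 lists two changes from the protocol, to the treatment-emergent period and to baseline. It lists no change to the DLT rate.

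**The concern.** The primary objective rests on DLTs, and the DRC is told to consider the weekly rate when it judges the titration regimen. The protocol's measure is an event rate: a patient with two DLTs adds two. The SAP's measure adds one for that patient and keeps a pooled time denominator. The rate delivered would therefore not be the one the protocol promises, and it could differ in one direction only, downward. Nothing in the SAP tells the reader of the output that the meaning has changed.

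The denominator adds a second uncertainty. The protocol names CORT125281. The SAP refers only to time on treatment, and protocol section 5 defines study treatment as CORT125281 and/or enzalutamide. If days on enzalutamide alone are counted, the rate falls further.

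**Working it through.** **Inputs from the documents**

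- Arm A: 12 DLT-evaluable patients (protocol 3.2.1, SAP 2.3).
- Window: 3 cycles of 28 days = 84 days = 12 weeks. SAP 8.8 equates 75% of doses with 63 days, and 0.75 × 84 = 63, so its window is indeed 84 days.
- Full follow-up of Arm A: 12 × 12 = 144 patient-weeks.

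**Inputs not in the documents (assumed)**

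- k, patients with at least one DLT: 4.
- m, mean DLTs per affected patient: 1 to 3.

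The plan states no weekly DLT rate, so there is no figure of its own to reproduce.

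**Formulas.** Let E be weeks of exposure to CORT125281 and T the SAP's weeks on treatment.

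- Protocol rate = k × m / E
- SAP rate = k / T
- SAP rate ÷ protocol rate = (1/m) × (E/T)

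**Equal denominators (E = T = 144).** The shortfall is 1 − 1/m, and k cancels.

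| m | Protocol rate | SAP rate | Shortfall |
|---|---|---|---|
| 1 | 4/144 = 0.0278 | 4/144 = 0.0278 | 0% |
| 1.5 | 6/144 = 0.0417 | 0.0278 | 33% |
| 2 | 8/144 = 0.0556 | 0.0278 | 50% |
| 3 | 12/144 = 0.0833 | 0.0278 | 67% |

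If 0, 1, 2, 3 or 4 of the four affected patients have two DLTs and the rest have one, the shortfall is 1 − 4/(4 + j), with j the number who have two: 0%, 20%, 33%, 43% and 50%.

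**Is m above 1 plausible?** Protocol 1.3.2.1 reports that both patients in Segment 1 Cohort 1 had DLTs, one of them with concurrent Grade 3 fatigue and Grade 3 musculoskeletal pain. If each term counts as a DLT, that is 3 DLTs in 2 patients, m = 1.5. The documents do not say how concurrent terms are counted, and this was another segment, so it shows only that m above 1 can happen.

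**Unequal denominators (E < T).** Protocol 5.7.1.1 lets a patient resume enzalutamide before CORT125281 after an interruption. Suppose each of the four affected patients has 4 such weeks and the SAP counts them. Four weeks is a generous choice: section 5.7.2 limits a toxicity hold to 28 days, and section 5.7.1 withholds both drugs at the start of a hold. Then E = 144 − 4 × 4 = 128.

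- m = 1: protocol 4/128 = 0.0313, SAP 4/144 = 0.0278, shortfall 1 − 128/144 = 11%.
- m = 2: protocol 8/128 = 0.0625, SAP 0.0278, shortfall 1 − (1/2)(128/144) = 56%.

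If the SAP means exicorilant days, this second component disappears.

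**The case against.** The strongest reply is that little depends on this rate. The 33% criterion is a percentage and does not fit a per-week quantity. SAP 8.8 separately defines a DLT rate as the proportion of DLT-evaluable patients with a DLT, which is the form that does fit. It also tabulates the number of DLTs by regimen, arm and highest dose level, so the protocol's numerator is in the same output. With about 16 evaluable patients, the DRC can in effect look at each DLT. All of this stands, and it keeps the impact modest. It does not fully repair the rate: exposure in SAP 8.7 runs to the last dose of each drug and is not limited to the DLT-evaluation period, so the protocol's denominator is not clearly among the planned outputs.

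The denominator can also be read benignly. It is limited to the first 12 weeks, and the regimens in SAP 8.8 are exicorilant doses plus enzalutamide, to which enzalutamide-only time does not belong. That is fair: the wording is ambiguous, not shown to be wrong.

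Three stronger readings are tempting, and the documents do not support them.

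- **That the understatement is at most half.** Half is the value at m = 2 on equal denominators. It is zero at m = 1 and 67% at m = 3.
- **That a patient who stops CORT125281 because of a DLT generally goes on adding enzalutamide weeks.** Protocol 5.7.1.1 does say "if CORT125281 is discontinued, enzalutamide will be continued", but only for patients who have not progressed on enzalutamide or a second-generation anti-androgen. The next item stops both drugs in those who have. Segment 2 enrols patients whose PSA is rising on enzalutamide. The documents do not say whether that counts as progression for this rule, but it may limit such time considerably.
- **That counting time after the first DLT is itself a departure.** With four first DLTs at week 6 and dosing continued, 4/144 is 17% below 4/120 (8 × 12 + 4 × 6 = 120). The protocol's own denominator also includes time after a DLT, so this is not a difference between the two documents.

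**Conclusion.** The inconsistency is real and rests on the text alone. SAP 8.8 counts patients, while protocol 9.5.4, protocol 5.4.2 and SAP 2.3 count DLTs, and section 13 is silent. On equal denominators the two rates agree if every affected patient has exactly one DLT. Otherwise the SAP rate is lower by 1 − 1/m: 33% at 1.5 DLTs per affected patient and 50% at 2. The sizes are illustrations on assumed m, not predictions or bounds. Any further lowering through the denominator depends on whether enzalutamide-only days are counted, which the SAP leaves open.

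A reader might infer that the regimen decision would be biased against the 33% criterion. The documents do not show that, because the patient-proportion rate in SAP 8.8 is unaffected. The point is worth correcting because the DRC is told to weigh the weekly rate and the correction is cheap.

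**What to change.** In SAP 8.8, define the DLT rate per patient-week as in protocol 9.5.4: numerator, the number of DLTs; denominator, weeks of exposure to exicorilant within the DLT-evaluation period, with the drug named. If a patient-based weekly rate is also wanted, give it a separate label and declare it in section 13.

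The cost is a sentence or two in the SAP and a small programming change. DLT counts and exicorilant dosing dates are already collected, so no new data are needed. The change should be made before Segment 2 is unblinded.
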